# 6.3 Data Management

#### 6.3.1 Data Source

• OSDI is a validated PRO tool which consists of 12-item questionnaire evaluating a patient's dry eye symptom severity using a 6-point scale. All

Version date: 02 February 2023

participants will complete an OSDI Questionnaire. The purpose of this assessment is to capture a range of ocular surface symptoms, including symptoms related to dry eye, their severity, and their impact on the participant's ability to function, scaled into a 0 (no disease) to 100 (maximum severity of disease) score. Participants will complete the OSDI at Screening Visit, Baseline Visit, Day 14 and Day 30/Early exit.

• Patient Eye Drop Experience Survey will evaluate the short- and long-term subjective eye drop experience in relief and tolerability with the study eye drops using a VAS. All participants will complete the Patient Eye Drop Experience Survey Day 14 and Day 30/Early exit. Participants should be instructed to mark a vertical line on the anchored VAS that best describes their agreement with the statements within the questionnaire. The vendor Lumanity will then convert the participant's response to a numerical value (0 to 100). This is an overall evaluation, not per eye.

Current Symptom Survey will evaluate the subjective onset of action of the eye drop as it pertains to relief and tolerability using a VAS. All participants will complete the Current Symptom Survey at Day 1. Survey will be administered at T0 (pre-dosing), T30s, T1min, T3min and T5min post-dosing. Participants should be instructed to mark a vertical line on the anchored VAS that best describes their agreement with the statements within the questionnaire. The vendor Lumanity will convert the participant's response to a numerical value (0 to 100). This is an overall evaluation, not per eye. Study Product Usage Questionnaire will evaluate the product usage and compliance of study drug. All participants will complete the Study Product Usage Questionnaire at Day 14 and Day 30/Early exit. The vendor Lumanity will collect the data.

Version date: 02 February 2023

#### 6.3.2 Data Elements to Be Obtained

### 6.3.2.1 Prospective Data Component

### **OSDI**

The OSDI will be administered to patients at Screening Visit, Baseline Visit, Day 14 and Day 30/Early exitpost-ABBV-444 administration. The OSDI can be found in Appendix C.

# **Patient Eye Drop Experience Survey**

The Patient Eye Drop Experience Survey will be administered to patients at Day 14 and Day 30/Early exit, post ABBV-444 administration. The Patient Experience Survey can be found in Appendix D.

### **Current Symptom Survey**

Current Symptom Survey will be administered to patients on Day 1; T0 (pre-dosing), T30s, T1min, T3min and T5 min post-dose at the study site. The Current Symptom Survey can be found in Appendix E.

#### **Study Product Usage Questionnaire**

Study Product Usage Questionnaire will be administered to patients at Day 14 and Day 30/Early exit. The Study Product Usage Questionnaire answers will be recorded in the Data Collection Forms, Appendix B.

#### 6.3.3 Data Collection Methods

Eligible participants will be provided an IRB approved ICF. The physician or their staff will record any relevant patient information per standard of care (SOC) into their local patient health record keeping system. Patient eligibility, required demographics and additional visit information will be recorded in supplied paper study data forms (Appendix B). In addition, any applicable safety reporting will be recorded on the

Version date: 02 February 2023

supplied paper AE/SAE forms (Appendix F) and follow the process outlined in Section 9.3.

Paper English versions of the OSDI, Current Symptom Survey, Patient Eye Drop Experience Survey and the Study Product Usage Questionnaire will be provided to the site and labeled with a unique patient number for completion by the patient. Consented patients who meet all inclusion and none of the exclusion criteria will be allowed to complete these questionnaires at the specified study days. The participating site will be asked to send the completed questionnaires regularly to Lumanity (see Appendix A).

### 6.4 Treatments

#### 6.4.1 Treatments Administered

During the treatment phase, each patient will be instructed to instill 1 to 2 drops of ABBV-444 in each eye, as needed, but at least 2 times daily. The same vial can be used for both eyes and should be used one time only. The used vial should then be stored in the supplied collection bag and returned to the site at the next scheduled visit for drug accountability, Section 6.4.5.

Patients are to be instructed during Screening Visit to not use any eye drops (artificial tears or prescription) for at least 4 hours prior to their Baseline Visit. If the patient is concurrently using allowed RESTASIS or IOP-lowering therapy drops during the study treatment they are to be instructed to wait a minimum of 15 minutes between administration of study drug and the allowed concomitant eye drops.

Version date: 02 February 2023

Table 2. Identity of Investigational Product

Investigational Product	ABBV-444
Mode/Route of Administration	Ophthalmic
Dosage Form	Solution, Single Dose Vial
Strength	Carboxymethylcellulose Sodium and Glycerin Ophthalmic Solution Preservative Free with Potassium Chloride
Frequency of Administration	Minimally BID
Storage Conditions	Between 15°C and 30°C (59 – 86°F)

### Packaging and Labeling

ABBV-444 will be packaged in vial/carton/resealable pouch with quantities sufficient to accommodate study design. Each vial/carton/resealable pouch will be labeled per local regulatory requirements. The labels must remain affixed to the vial/carton/resealable pouches. All blank spaces should be completed by site staff before dispensing to subject.

# 6.4.2 Storage and Disposition of Study Drug

ABBV-444 must be stored as described in table above. The investigational products are for investigational use only and are to be used only within the context of this study. The study drugs supplied for this study must be maintained under adequate security and stored under the conditions specified on the respective drugs' label until dispensed for subject use or destroyed on site as appropriate.

# 6.4.3 Selection and Timing of Dose for Each Patient

ABBV-444 will be self-administered bilaterally at minimum twice a day (BID) Day 1 through Day 30/Early exit. A single dose vial will be used to administer the eye drops. One single dose vial should be used bilaterally, for both eyes. If the patient feels it necessary to obtain better relief, ABBV-444 can be administered as needed (PRN) bilaterally.

Version date: 02 February 2023

# 6.4.4 Study Drug Usage for Each Patient

The 2-question Study Eye Drop Usage Questionnaire will be completed by each patient at Day 14 and Day 30/Early exit to capture the date and time of their last study drug administration and their overall compliance to study drug usage.

Question 1: "What date and time did you last use your study eye drops?"

Question 2: "On average, how many times did you administer the eye drops per day?"

Sites should review each patient's response to ensure that the last administration of their study drug was  $\geq 4$  hours from the start of completing this questionnaire and that they are using their study eye drops at minimum 2 times per day. Should either of the patient's responses be out of compliance, the site should discuss with the patient to ensure they dose correctly from that point forward.

# 6.4.5 Study Drug Accountability

The investigator or his representative will verify that study drug supplies are received intact and in the correct amounts. This will be documented by signing and dating the Proof of Receipt or similar document. The investigator or his designated representatives will dispense study drug only to patients enrolled in the study. A current (running) and accurate inventory of study drug will be kept by the investigator and will include shipping invoices and the date on which study drug is allocated to patients, as well as used and unused study drug returned by patients. An overall accountability of the study drug will be performed and verified by the investigator or his representative throughout the study until its completion. Upon completion or termination of the study, all original containers (containing used and unused study drug) will be destroyed on site per instructions supplied by AbbVie. All study drug accountability logs will be sent to Lumanity, per contact information found in Appendix A.

Version date: 02 February 2023

# 7.0 Statistical Methods, Sample Size and Analysis Plan

Analysis of all data will be descriptive. Biometrical analysis will be conducted based on subject demographics. Arithmetic mean, median, standard deviation (SD), standard error of the mean (SEM), interquartiles, minimum, and maximum will be used for the description of the data. Descriptive p-values (paired t-test) will be calculated for changes during the observation period, if adequate.

# 7.1 Analysis Populations

The full analysis set (FAS) will consist of all subjects who are study eligible based on the inclusion and exclusion criteria and complete 30 days of treatment for this study.

# 7.2 Sample Size and Justification

This study is not a confirmatory study with hypothesis testing. At least 40 subjects will be enrolled in this study based on a feasibility assessment. Assuming a non-response rate of 10% at Day 30, there would be about 36 evaluable subjects.

### 7.3 Statistical Analysis Plan

### 7.3.1 General Approach

Demographic and other baseline subject characteristics will be summarized. Descriptive statistics (such as mean, standard deviation, median, minimum and maximum) will be presented for each continuous variable. Categorical variables will be displayed using frequency counts and percentages. Patients Demographics, Disease Characteristics, Treatment Patterns, and Treatment Discontinuation

Demographics and other baseline characteristics of the study subjects will be summarized descriptive statistics (such as mean, median, standard deviation, median, standard error of the mean (SEM) interquartiles, min and max) will be presented for each continuous variable, Categorical variables will displayed using frequency counts with percentages.

Version date: 02 February 2023

# 7.3.3 Primary Analysis

The analysis is based on full analysis set (FAS). The primary endpoint is the change of OSDI score from baseline at Day 30. The change of OSDI score will be summarized using descriptive statistics: mean, median, standard deviation, standard error of the mean (SEM), interquartiles, min and max. A descriptive p-value (paired t-test) will be calculated for the change of OSDI score if the data is adequate.

### 7.3.4 Secondary Analysis

The secondary endpoints of interest are the Patient Eye Drop Experience Survey score at Day 30 and the change of Current Symptom Survey score from baseline at T5min post-dose. The score of each item in the Patient Eye Drop Experience Survey at Day 30 and the change of Current Symptom Survey at T5min will be summarized using descriptive statistics: mean, median, standard deviation, standard error of the mean (SEM), interquartiles, min and max. In the meanwhile, one bar plot for the mean of the score with 95% confidence interval will be made for each of the secondary endpoints. The change of Current Symptom Survey score from baseline at T5min will be summarized using the same descriptive statistics. A descriptive p-value (paired t-test) will be calculated for the change of VAS score if the data is adequate.

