#### 5.1 **Research Question**

There is no formal hypothesis as the nature of this study is to describe the effect of ABBV-444 on symptoms relief of dry eye, such as burning, irritation and, discomfort due to eye dryness, the onset of action of relief and the patient experience across various timepoints.

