#### 5.2.2 **Secondary Objectives**

The secondary objective is to investigate the patient eye drop experience of ABBV-444 and the eye drop onset of action using a VAS-Current Symptom Survey.

Version date: 02 February 2023

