# 5.3.2 Secondary Endpoints

- Patient Eye Drop Experience scores at Day 30
- Change from baseline in symptom scores within 5 mins post administration of ABBV-444

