# 6.0 Study Design

### 6.1 Overall Design

[figure not shown]
This prospective, minimally interventional study will aim to describe the effect of ABBV-444 on relieving dry eye symptoms, such as burning, irritation, discomfort due to eye dryness (via the OSDI scoring tool), the patient experience (via a Patient Eye Drop Experience Survey) and the onset of action of the eye drop (via the Current Symptom Survey) across various timepoints (Figure 1). This will be an open-label, 1-arm study in which eye drops will be administered bilaterally as needed but minimally twice a day. Approximately 40 patients are planned to be enrolled at 1 site. A screening period of up to 6 days will be conducted prior to the Baseline Visit. Patients will be instructed to not administer any drops at least 4 hours prior to Baseline Visit. There will be three surveys administered to the subjects throughout the course of the study at the following timepoints:

Version date: 02 February 2023

- 1. OSDI will be given at Screening Visit, Baseline, Day 14 and Day 30/Early exit; and
- 2. Patient Eye Drop Experience Survey at Day 14 and Day 30/Early exit; and
- 3. Current Symptom Survey at Day 1; T0 (pre-dosing), T30s, T1min, T3min and T5min post-dose.
- 4. Study Product Usage Questionnaire at Day 14 and Day 30/Early exitStudy treatment is 30 days where OSDI scores, Patient Eye Drop Experience Survey scores and Current Symptom Survey scores will be obtained at the time points listed above. To assess product usage and compliance, the Study Product Usage Questionnaire will be administered at the time points listed above. Data will be collected via a paper questionnaire, sent to Lumanity where outcomes will be computed as mean changes from their baseline values.

Figure 1. Study Schematic

**Table 1.** Study Activities

It is recommended these procedures are completed in order listed at each study visit.

Version date: 02 February 2023

Study Visit	Screening (Day -7)	Baseline (Day 1)	Day 14	Day 30/Early Exit
Visit Window	(-7 to -1 days)		(+/- 3 days)	(+/- 3 days)
Written informed consent	X			
Urine pregnancy test (for females of childbearing potential only)	X			
Demography	X			
Adverse Event Assessment	X	X	X	X
Study Product Usage Questionnaire			X	X
OSDI Questionnaire	X	X	X	X
Biomicroscopy	X	X		
Tear Breakup Time (with fluorescein)	X			
Corneal staining (modified NEI grading scheme, with fluorescein)	X	X		
Conjunctival staining (modified NEI grading scheme, with lissamine green)	X	X		

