# At Day 1: T0 (pre-dose), 30 secs post-dose, 1 min post-dose, 3 min post-dose, 5 min post-dose:

Current Symptom Survey will be completed by each patient to measure their ocular symptoms at current moment. Patients should be instructed to mark a vertical line on the anchored VAS that best captures how their eyes are feeling at the current moment. A trained member of the study personnel will then use the provided ruler to convert the patient's response to a numerical value (0 to 100). This is an overall evaluation, not per eye. The questionnaire will read as follows (note: the VAS scales will be an actual scale and not just text as indicated below for the purposes of this protocol).

Think about how your eyes are feeling right now. Then, using the scales provided below, please mark a vertical line that best describes your experience with these symptoms:

1. Burning/stinging due to dryness of the eye (VAS anchors: 0 = no burning/stinging,

100 = maximum burning/stinging)	
Strongly Disagree ———————————————————————————————————	Strongly Agree

 
Grittiness/foreign body sensation due to dryness of the eye (VAS anchors: 0 = no grittiness/foreign body sensation, 100 = maximum grittiness/foreign body sensation)
 
	
Strongly Disagree ———————————————————————————————————	Strongly Agree
3. Eye Dryness (VAS anchors: 0 = no dryness, 100 = maximum dryness)	
Strongly Disagree —	Strongly Agree

 
Blurry/fluctuating vision due to dryness of the eye (VAS anchors: 0 = no blurry/fluctuating vision, 100 = maximum blurry/fluctuating vision)
 
	
Strongly Disagree ———————————————————————————————————	Strongly Agree

 
Overall discomfort due to dryness of the eye (VAS anchors: 0 = no pain/discomfort, 100 = maximum pain/discomfort)
 
	
Strongly Disagree -	Strongly Agree

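### Section 7.3.4 names only the 5-minute time for the Current Symptom Survey, so the specified analysis cannot show when relief begins

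*Combined protocol and SAP*

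**What the plan says.** Section 5.1 sets out to describe, among other things, "the onset of action of relief and the patient experience across various timepoints". The secondary objective in 5.2.2 includes "the eye drop onset of action using a VAS-Current Symptom Survey", and 6.3.1 gives onset of action, for both relief and tolerability, as the purpose of this survey. The endpoint in 5.3.2 is "Change from baseline in symptom scores within 5 mins post administration of ABBV-444", which fixes no single time.

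Section 6.1 schedules the survey on Day 1 at T0, T30s, T1min, T3min and T5min and states that "Current Symptom Survey scores will be obtained at the time points listed above". Appendix E says "Current Symptom Survey will be completed by each patient to measure their ocular symptoms at current moment" and then lists five separate VAS items, the last being "Overall discomfort due to dryness of the eye". It gives no rule for combining them.

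The analysis text is narrower. Section 7.3.4 defines the endpoint as "the change of Current Symptom Survey score from baseline at T5min post-dose" and then specifies summaries for "The score of each item in the Patient Eye Drop Experience Survey at Day 30 and the change of Current Symptom Survey at T5min". A later sentence repeats the summary, again at T5min. Section 7.3.5 covers Day 14: the Experience Survey score and the OSDI change. It ends by giving the paired t-test to a change in VAS score.

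**The concern.** To describe onset one needs the course of symptoms over the first minutes. The study collects that course, but the section that specifies the analysis uses only its last point. Two quite different products, one acting within 30 seconds and one acting only between 3 and 5 minutes, could give the same T5min result. The survey also concerns tolerability, and its items include burning/stinging and blurred vision. A brief worsening after instillation that cleared by 5 minutes would not show.

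Because the earlier times rest on general wording, whether they are reported, and by item or as a total, could be settled after the data are seen. A report giving T5min alone and a report giving a favourable selection of times could both claim to follow the plan.

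**Working it through.** The plan gives no numerical figure on this point. Its one related figure reproduces: 40 × (1 − 0.10) = 36 evaluable subjects (7.2).

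**What is collected (6.1, Appendix E)**

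- Items: burning/stinging, grittiness/foreign body sensation, dryness, blurry/fluctuating vision, overall discomfort = 5.
- Post-dose times: T30s, T1min, T3min, T5min = 4.
- Item-by-time changes from T0: 5 × 4 = 20.

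**What 7.3.4 names**

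- T5min appears three times: once for the endpoint and twice for its summaries. The bar plot and the t-test follow from that endpoint.
- By item: 5 × 1 = 5 changes named; 20 − 5 = 15 (75%) not named.
- As a total: 1 of 4 named, 3 not.

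**What the times can show about onset**

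| Times used | Intervals in which onset of mean relief can be placed |
|---|---|
| T5min only | 0–300 s (width 300 s) |
| All four | 0–30, 30–60, 60–180, 180–300 s (widths 30, 30, 120, 120 s; sum 300 s) |

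This placement is subject to sampling error. With 36 subjects, the half-width of a 95% confidence interval for a mean change is t(0.975, 35)/√36 = 2.030/6 = 0.34 SD of the change; with 40 it is 0.32 SD. The documents give no SD, so this cannot be put in VAS points.

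**What the general wording covers**

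- 6.1 says survey outcomes are computed as mean changes from baseline, after listing all the times.
- 7.0 makes the analysis of all data descriptive and provides paired t-tests for changes over the observation period, if adequate. It names no times and does not define adequate.
- 7.3.1 promises descriptive statistics for every continuous variable, but in a paragraph on demographics and baseline characteristics.

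These provisions are consistent with summaries at the earlier times. None names an earlier time in an analysis, and the specific section fixes the endpoint at T5min.

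**Item or total.** In 7.3.4 the per-item wording stands next to the Experience Survey; the Current Symptom Survey is referred to by a single score. Appendix E supports only item-level scores.

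**Day 14 VAS change (7.3.5)**

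| Instrument | VAS? | Given at | Change from baseline at Day 14? |
|---|---|---|---|
| Current Symptom Survey | Yes | Day 1 only | No |
| Experience Survey | Yes | Day 14, Day 30/early exit | No (no pre-treatment value) |
| OSDI | No | Screening, Baseline, Day 14, Day 30/early exit | Yes |

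VAS changes from baseline that can be computed at Day 14: 0. The t-test sentence is identical to the last one in 7.3.4, which suggests carry-over; that is an inference.

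**The case against.** The strongest reply is that the plan already covers the earlier times. Section 6.1 lists them and commits to mean changes from baseline, and 7.0 applies to all data the same statistics that 7.3.4 lists. Both say that this will be done, not that it may be. This stands to the extent that it would be wrong to say the earlier times have no analysis. It does not close the gap, because 6.1 speaks of computation rather than reporting and neither section ties an analysis to an earlier time.

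Second, naming one time is a sound way to fix a headline result, and the Synopsis words the objective as immediate symptom relief, which a T5min change addresses. That is a good reason to keep T5min as the headline. It does not answer the onset wording in 5.1, 5.2.2, 6.1 and 6.3.1.

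Third, the item-or-total doubt can be read away: 5.3.2 speaks of scores in the plural, no total is defined, and the per-item phrase in 7.3.4 may govern both surveys. Item-level analysis is indeed the likelier intention, but it should be stated.

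Fourth, the counts measure neither bias nor lost precision, and a plotted time course does not by itself define when relief has begun. Both points are fair. The counts show only how much is left unspecified, and the plot describes onset without declaring a time.

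Finally, the study has no formal hypothesis. That limits the consequences but does not remove the point, since description of onset is itself an aim.

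**Conclusion.** The concern holds. The analysis specified in 7.3.4 uses one of four post-dose times and cannot show when relief begins or reveal a transient early worsening, although the data for both are collected. By item, 15 of 20 changes are left to general wording. This count assumes item-level analysis; with a total it is 3 of 4.

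The change should be made, but the point is of moderate weight. The study is descriptive, the primary endpoint is untouched, and no error rate or sample size changes. The 7.3.5 wording is a separate minor error in one descriptive p-value for an exploratory endpoint. Section 7.0 already allows a paired t-test on the Day 14 OSDI change, so it adds nothing to the weight.

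**What to change.** In 7.3.4:

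- For each of the five items, summarise the change from T0 at T30s, T1min, T3min and T5min with the descriptive statistics already listed.
- Plot the mean change over time with 95% confidence intervals, one panel or line per item.
- Keep T5min as the headline result, and state that p-values for this survey are given at T5min only, so that the general t-test provision in 7.0 does not leave the earlier times open.
- If a total score is intended instead, state how it is formed.
- If the report is to name an onset time, state the rule for it beforehand.

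In 7.3.5, make the Day 14 paired t-test refer to the OSDI change from baseline instead of a VAS change.

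The cost is SAP wording, extra table rows and one plot, with no new data. The downside is more descriptive summaries, 20 instead of 5 by item. Holding the p-values at T5min keeps their number at 5. For illustration, if a 0.05 level were applied (the plan sets none) and tests were independent, the chance of at least one false positive would be 1 − 0.95^5 = 0.23 with 5 tests and 1 − 0.95^20 = 0.64 with 20. Correlation between items and times would change these figures.
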